21 SEP 2022

Version 2

1. Glossary

Term	Definition	
AE	Adverse Event	
MyCareLink®	Network (registered trademark of Medtronic)	
	designed to receive and store transmitted	
	LINQ [™] /LINQII [™] ICM data	
CFR	Code of Federal Regulation	
CIP	Clinical Investigation Plan	
CRF	Case Report Form	
СТА	Clinical Trial Agreement	
CV	Cardiovascular	
eCRF	Electronic Case Report Form	
EC/IRB/HREB/Ethics Board	Ethics Committee	
FDA	Food and Drug Administration	
GCP	Good Clinical Practice	
ICD	Implantable Cardiac Defibrillator	
ICF	Informed Consent Form	
ICM	Insertable Cardiac Monitor	
ms	milliseconds	
SAE	Serious Adverse Event	
VitalPatch [®] RTM	External, wearable patch (registered trademark of	
	Vital Connect, Inc.) that provides up to 7 days of	
	monitoring in order to monitor parameters such as	
	ECG, heart rate variability, respiratory rate,	
	temperature, activity, and posture.	

Medtronic Business Restricted

21 SEP 2022

Version 2

Page 6 of 48

Medtronic

2. Synopsis

Title	LINQ QT Study		
Clinical Study Type	Prospective, non-randomized, multi-center, observational, post-market clinical study.		
Product Name	LINQ TM , LINQII TM		
Sponsor	Medtronic		
	[name]		
	[name]		
Local Sponsor	Medtronic Research and Technology		
	[name]		
	[name]		
Indication under	QT interval changes due to antiarrhythmic drug loading		
investigation			
Investigation	The purpose of this study is to determine if QT interval changes are detected during and		
Purpose	after antiarrhythmic drug loading by the designed QT detection algorithm from		
	LINQ [™] /LINQII [™] ECG. The QT intervals before and after antiarrhythmic loading will be		
	compared for all patients to analyze QT changes that may be caused due to antiarrhythmic		
	drugs.		
Product Status	Market-Released		
Primary	The primary objective of the study is to determine if QT changes can be detected from		
Objective(s)	LINQ [™] ECG that may occur during and after antiarrhythmic loading. The QT intervals before		
and/or	and after antiarrhythmic loading will be compared for all patients to analyze QT changes		
Endpoint(s)s	that may be caused due to antiarrhythmic drugs.		
Study Design	The LINQ [™] QT Study is a prospective, non-randomized, multi-center, observational, post-		
	market clinical study.		
Randomization	Non-randomized		
Sample Size	The study is expected to be conducted at up to three study sites located in the United States		
	and will enroll up to twenty study subjects. It is anticipated that if one study site cannot		
	enroll at least 3 subjects per month, that additional study sites will be included to meet the		
	total enrollment target of twenty subjects.		
Inclusion/Exclusion	Inclusion Criteria:		
Criteria	 Patients implanted with LINQTM/LINQIITM prior to the study enrollment (no more than 50% patients implanted with LINQIITM), but no greater than 2 years for LINQTM or 3 		
	years for LINQII [™] , or patients who are indicated to receive a LINQ [™] /LINQII [™] implant		
	at least 7 days prior to antiarrhythmic drug loading		
	Patients who are scheduled to receive antiarrhythmic drug loading		
	• Up to 20% of patients enrolled in the study can have permanent and persistent AF		
	 Age 10-00 Patient is willing and able to comply with the protocol including follow-up visits and 		
	performing Holter recordings and patient activation transmissions		

Medtronic Business Restricted

LINQ QT Study Clinical Investigation Plan						
21 SEP 2022	Version 2 Page 7 of 48			Medtronic		
	 Exclusion Criteria: Patients who have a contraindication to long-term antiarrhythmic therapy Patients not suitable for long-term antiarrhythmic therapy 					
	 Patients with a previo cardiac resynchroniza defibrillator (ICDs)) Co-enrollment in anoth during the course of the 	tion requir er study or p is clinical stu	ing > 40% pac blanning to partici	tion (i.e., cardi cing, implanta pate in a concu nfound the resu	ac pacemaker or ble cardioverter rrent device study lts	
Study Procedures and Assessments	Study Procedure	Baseline	Index Antiarrhythmic Loading Event	(Optional) 2, 4, 8 week	90-day Visit/Study Exit	
	Patient Informed Consent	Х				
	Inclusion/Exclusion Assessment	Х				
	Cardiovascular (CV) and Medical History	Х				
	Demographics	Х				
	Physical Exam	Х	Х	Х	X	
	Blood Labs	Х	Х	Х	X	
	CV Symptoms*optional	Х	Х	Х	X	
	Medications	Х	Х	Х	Х	
	12-Lead ECG	Х	Х	Х	Х	
	2D Echocardiogram*optional	Х				
	Holter/ VitalPatch [®] RTM		Х	Х	X	
	MyCareLink [®] Daily Manual Transmissions	Х	х	Х	X	
	Patient Activations		Х	Х	X	
Study exit X Serious, Cardiovascular- related Adverse Events X X					X	
		Х	X			
	Study deviations Report upon occurrence					
Safety Assessments	There are no defined safety end not to demonstrate safety or ef	ndpoints in the LINQ QT study as the purpose of the study is effectiveness. Cardiovascular-related (CV) adverse events that				

Medtronic Business Restricted

LINQ QT Stu	udy Clinical Investigation F	Plan			
21 SEP 2022	21 SEP 2022 Version 2 Page 8 of 48			Medtronic	
	result in hospitalization due to anti-arrhythmic loading will be collected throughout the duration of the subject's participation in the study, beginning after the initial in- hospital/out-patient anti-arrhythmic loading.				
Statistics	Since the study will be exploratory in nature and the study objectives are descriptive, no clinical endpoints will be developed. LINQ™/LINQII [™] derived data will be summarized using descriptive statistics.				

3. Introduction

3.1 Background

The QT interval on the electrocardiogram (ECG) has gained clinical importance, primarily because prolongation of this interval can predispose to a potentially fatal ventricular arrhythmia known as torsades de pointes, which could in turn lead to sudden cardiac death [1]. Multiple factors have been implicated in causing QT prolongation and torsades de pointes. Among these, an important risk factor for long QT syndrome is the use of QT prolonging drugs. A QT interval greater than 500 milliseconds (ms) has been shown to correlate with higher risk of torsades de pointes.

There are several commonly used medications that could lengthen QT and cause QT prolongation. One such class of medications are antiarrhythmic drugs which are used to treat heart rhythm disorders. These drugs are frequently prescribed in everyday clinical practice for the management of atrial fibrillation (AF) that affects nearly 1–2% of the general population [2,3]. The commonly used antiarrhythmics for AF rhythm control management belong to Vaughan Williams' classes, Ic and III. Both these medication categories are well known to influence ventricular depolarization and repolarization, alter QT and corrected QT interval (QTc) intervals on surface ECG and affect to variable extents the left ventricular (LV) function [4–10].

There are several studies which have assessed the effect of antiarrhythmic drugs on QT interval prolongation. One such study [11] revealed significant QTmax and QTc interval prolongation following Sotalol (from 424 ± 40 ms to 460 ± 57 ms and from 446 ± 35 ms to 474 ± 48 ms, respectively, both p < 0.01) and Amiodarone (from 437 ± 41 ms to 504 ± 39 ms and from 469 ± 35 ms to 527 ± 50 ms, respectively, both p < 0.01). Another study [12] revealed a significant mortality benefit when dofetilide was used in patients with baseline QTc intervals less than 429 ms (risk ratio 0.3), while an increase in mortality was seen with dofetilide therapy in patients with baseline QTc intervals greater than 429 ms (risk ratio 1.3) [13].

Currently, there is no reliable way for continuous and long-term monitoring of QT intervals in patients undergoing antiarrhythmics drug loading. An implantable cardiac monitor which can continuously monitor QT intervals in patients taking QT prolonging drugs can enable clinicians to track day-to-day variability in the QT intervals and also study long-term QT trends in patients.

Medtronic Business Restricted

21 SEP 2022

Version 2

Page 9 of 48

The Reveal LINQ[™] and LINQII[™] devices are small, leadless cardiac monitoring systems that can be inserted subcutaneously in the chest with a minimally invasive procedure and provide continuous monitoring of diagnostic parameters for up to 3 years and 4 years respectively. An algorithm [14] has been developed and validated which can continuously measure QT intervals for every beat using LINQ[™] ECG. This study is aimed at determining if QT interval changes can be detected during and after antiarrhythmic drug loading by the designed QT detection algorithm from LINQ[™] ECG.

3.2 Purpose

The purpose of this study is to determine if QT interval changes are detected during and after antiarrhythmic drug loading by the designed QT detection algorithm from LINQ[™] ECG. The QT intervals before and after antiarrhythmic loading will be compared for all patients to analyze QT changes that may be caused due to antiarrhythmic drugs.

4. Objectives and/or Endpoints

4.1 Objectives

4.1.1 Primary Objective

The primary objective of the study is to determine if QT changes can be detected from LINQ[™] ECG that may occur during and after antiarrhythmic loading. The QT intervals before and after antiarrhythmic loading will be compared for all patients to analyze QT changes that may be caused due to antiarrhythmic drugs.

5. Study Design

The LINQ[™] QT Study is a prospective, non-randomized, multi-center, observational, post-market clinical study. The study is expected to be conducted at up to three study sites located in the United States and will enroll up to twenty study subjects. It is anticipated that if one study site cannot enroll at least 3 subjects per month, then additional study sites will be included to meet the total enrollment target of twenty subjects.

Study subjects implanted with LINQ[™]/LINQII[™] (no more than 50% patients implanted with LINQII[™]), but no greater than 2 years for LINQ[™] or 3 years for LINQII[™], or patients who are indicated to receive a LINQ[™]/LINQII[™] implant at least 7 days prior to antiarrhythmic drug loading will be considered for enrollment in this study.

Medtronic Business Restricted

LINO OT Study Clinica	I Investigation Dian		
		I	
21 SEP 2022	Version 2	Page 10 of 48	Medtronic

Figure 1: Study Flow Diagram

Medtronic Business Restricted

LINQ QT Study Clinical Investigation Plan			
21 SEP 2022	Version 2	Page 11 of 48	Medtronic

- I. Index Antiarrhythmic Loading Event
 - 1. Subjects with LINQ[™] Implants

2. Subjects with LINQII[™] Implants

II. Follow up period

Medtronic Business Restricted

LINQ QT Study Clinical Investigation Plan			
21 SEP 2022	Version 2	Page 12 of 48	Medtronic

- III. Follow up clinic visits
 - 1. Subjects with LINQ[™] Implants

2. Subjects with LINQII[™] Implants

Medtronic Business Restricted

21 SEP 2022

Version 2

5.1 Duration

Subjects will be followed until their 90 -day visit or until official study closure defined as when study data requirements have been satisfied per the Clinical Investigation Plan (CIP) and/or by a decision by Medtronic or the applicable external parties (i.e., IRB/Ethics Committee (EC) Regulatory Authority) whichever occurs first. The estimated total study duration is approximately 13 months, representing a 7-month enrollment period, at least 3 months of follow-up per subject and at least 3 months for data analysis.

5.2 Rationale

Safety will not be a primary focus of this study as 1) the study is only collecting observational data, 2) data collected will not be used to manage the treatment of subjects in the study, 3) data collection procedures other than those related to the LINQ[™]/LINQII[™] are not outside standard of care and 4) the safety profile of LINQ[™]/LINQII[™] is already well known.

6. Product Description

6.1 General

The Medtronic LINQ[™]/LINQII[™] ICM is an approved, programmable device that continuously monitors a patient's electrocardiogram (ECG) and other physiological parameters. The device records cardiac information in response to automatically detected arrhythmias and patient activation. The LINQ[™]/LINQII[™] device is indicated in the following:

US Indications:

- Patients with clinical syndromes or situations at increased risk of cardiac arrhythmias.
- Patients who experience transient symptoms such as dizziness, palpitation, syncope and chest pain that may suggest a cardiac arrhythmia.

Medtronic Business Restricted

21 SEP 2022	Version 2	Page 14 of 48	Medtronic
21 SEP 2022	Version 2	Page 14 of 48	Medtro

The study will be conducted using the components described in Table 1 below. All components of the LINQ[™]/LINQII[™] system are manufactured by Medtronic, Inc. Instructions for use of the devices used in this study are provided within their respective manuals.

Model Number	Component	Manufacturer	Investigational or Market- released
LINQ [™] /LINQII [™]	Reveal LINQ [™] /LINQII [™] Insertable Cardiac Monitor	Medtronic	Market-Released
SW026	2090 Programmer	Medtronic	Market-Released
MSW002 IOS (Apple)	LINQ [™] Mobile Manager (LMM)	Medtronic	Market-Released
MSW003 (Android) MSW004 IOS (Apple)	My CareLink Heart [™] App	Medtronic	Market-Released
24960	MyCareLink Relay™ Home Communicator	Medtronic	Market-Released
PA96000	Patient Assistant	Medtronic	Market-Released
24950	MyCareLink [®] Home Monitor	Medtronic	Market-Released
DR220	Holter	NorthEast Monitoring, Inc.	Market-Released

Table 1: Study Components

Descriptions of each component of the system are provided in the sections below.

6.1.1 Reveal LINQ[™]/LINQII[™] II Insertable Cardiac Monitor (ICM)

The Reveal LINQ[™]/LINQII[™] ICM is a small, leadless device that is inserted under the skin, in the chest. A specific recommended location is provided within the product manual. The device uses two electrodes on the body of the device to continuously monitor the patient's subcutaneous ECG. The device can store up to 30 min of ECG recordings from the patient-activated episodes and up to 27 min of ECG recordings from the patient.

Figure 2: Reveal LINQ[™]/LINQII[™] ICM

Medtronic Business Restricted

LINQ QT Study Cli	nical Investigation	Plan	
21 SEP 2022	Version 2	Page 15 of 48	Medtronic

6.1.2 2090 Programmer

The Medtronic CareLink[®] Programmer is used to program the Reveal LINQ[™]/LINQII[™] ICM to detect arrhythmias with various pre-specified characteristics. In addition, the programmer allows the physician to view, save, and print the ECG records currently held within the Reveal LINQ[™]/LINQII[™] ICM.

Figure 3: Medtronic 2090 Programmer

6.1.3 LINQ[™] Mobile Manager (LMM) and Patient Connector Head

The Reveal LINQ[™] Mobile Manager (LMM) clinician app is an application downloaded onto the clinic's tablet that communicates with the LINQII[™] ICM using BLE (the tablet downloaded with the clinician app is also referred to as the "LMM" within this document). The LMM provides the operator an interface to change device settings (programming), interrogate the collected data, and display real-time data such as ECG, telemetered EGM and Marker Channel information. The LMM can also be used to assess the system. The LMM uses the 24967 Patient Connector Head for communication.

6.1.4. My CareLink Heart[™] App

The MyCareLink Heart[™] mobile app (also referred to as "patient app") is an application downloaded onto the patient's smartphone/tablet (Android or IOS). The patient app installed on a mobile device transfers encrypted ICM device data between the inserted LINQ II[™] device and the CareLink[®] Network. The patient interacts with the patient app for initial setup, viewing status information, and recording symptoms. The patient app can be enabled to record cardiac information in the LINQ II[™] ICM while the patient is experiencing symptoms or immediately after a symptomatic event. The clinician uses the recorded information to determine if the symptoms were associated with a cardiac event.

Medtronic Business Restricted

21 SEP 2022

Version 2

6.1.5. MyCareLink Relay[™] Home Communicator

The MyCareLink Relay[™] Home Communicator (also referred to as "home communicator") is a stationary device that transfers encrypted data from/to the patient's inserted LINQ II[™] device to the CareLink[®] Network for patients unwilling or unable to use a smartphone/tablet. Data communication is via Bluetooth Low Energy (BLE) to the LINQ II[™] ICM and wireless GSM network to the CareLink[®] Network.

6.1.6 Patient Assistant

The Patient Assistant is a hand-held, battery-operated telemetry device that enables the subject, on experiencing symptoms potentially indicative of a cardiac event, to manually trigger the LINQ[™] ICM to collect and store an ECG record.

The Reveal Patient Assistant is intended for unsupervised patient use away from a hospital or clinic. The Patient Assistant activates the data management feature in the Reveal LINQ[™] ICM to initiate recording of cardiac event data in the implanted device memory.

The subjects will be asked to press the Patient Assistant whenever they experience increased difficulty of breathing not related to an activity.

Figure 4: Patient Assistant

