6.1.7 MyCareLink[®] Home Monitor

The MyCareLink[®] Home Monitor is a device that enables the device diagnostic data (which includes ECG data) to be transmitted directly from the implanted Reveal LINQ[™] device to the Medtronic CareLink[®] Network for review by the physician.

Medtronic Business Restricted

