7.3 Inclusion Criteria

- Patients implanted with LINQ[™]/LINQII[™] prior to the study enrollment (no more than 50% patients implanted with LINQII[™]), but no greater than 2 years for LINQ[™] or 3 years for LINQII[™], or patients who are indicated to receive a LINQ[™]/LINQII[™] implant at least 7 days prior to antiarrhythmic drug loading
- Patients who are scheduled to receive antiarrhythmic drug loading
- Up to 20% of patients enrolled in the study can have permanent and persistent AF
- Age 18-80
- Patient is willing and able to comply with the protocol, including follow-up visits, and performing Holter recordings and patient activation transmissions

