8.1 Schedule of Events

A patient will be considered enrolled in the study once they sign and date the Informed Consent. The subjects will be followed at in-office visits during study participation. In addition, the subjects will be completing daily manual device transmissions. The requirements for data collection and study procedures by visit are summarized in Table 2 below.

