8.8 Follow-up Visits

1. Subjects with LINQ[™] Implants

Medtronic Business Restricted

LINQ QT Study Clinical Investigation Plan			
21 SEP 2022	Version 2	Page 26 of 48	Medtronic

2. Subjects with LINQII[™] Implants

NOTE: Subjects may be compensated for completing the required daily activations.

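### Do the breathlessness-triggered presses and the blank Baseline cells for activations and Holter undermine the before/after QT comparison?

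*Protocol*

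**What the plan says.** The protocol touches on ECG capture in several places.

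- **Section 6.1.6 (Patient Assistant):** "The subjects will be asked to press the Patient Assistant whenever they experience increased difficulty of breathing not related to an activity". The device is described as triggering the LINQ ICM; Section 6.1.4 gives LINQ II a patient app instead.
- **Section 8.8 (Follow-up Visits):** the only visible body text is a closing note, "Subjects may be compensated for completing the required daily activations".
- **Synopsis, Study Procedures and Assessments:** the row "Patient Activations" and the Holter/VitalPatch row are empty at Baseline and marked at the index loading event, the optional visits and the 90-day visit. The 12-lead ECG and daily manual transmission rows are marked in all four columns.
- **Section 8.1:** "the subjects will be completing daily manual device transmissions", with the detail by visit left to Table 2.
- **Section 7.3:** subjects must be willing to comply, including "performing Holter recordings and patient activation transmissions".
- **Section 6.1 and Section 6.1.1:** "The device records cardiac information in response to automatically detected arrhythmias and patient activation", with storage for "up to 30 min of ECG recordings from the patient-activated episodes".
- **Section 6.1.7:** the home monitor enables "the device diagnostic data (which includes ECG data) to be transmitted directly" to the network.
- **Section 6.1.8:** the Holter's purpose in this study is to collect LINQ ECG so that QT can be measured, for up to 48 hours.

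Section 11.2.1 sets one objective, a comparison of QT before and after loading, summarised descriptively. Section 11 states that there is no hypothesis.

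**The concern.** There are two worries.

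The first is symmetry. A within-subject comparison is easiest to read when both periods hold the same kind of recording. If the device stores ECG only on a detected arrhythmia or a press, and presses start only at the index event, the pre-loading strips could be arrhythmia-triggered and the post-loading strips routine. Part of any QT difference would then reflect rate or rhythm at capture and not the drug. Strips that were never recorded before loading cannot be recovered later, and no analysis plan can repair that.

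The second is contamination. Breathlessness has no stated connection with QT. Presses made for that reason may come at an unusual heart rate and share the same store as the daily ones, and the visible text does not say whether they enter the QT summary.

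**Working it through.** The protocol states no figure on this point, so there is none to reproduce. The check is a reading of the passages, followed by a conditional calculation of what might be at stake.

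**1. Do the two press instructions conflict?** Section 6.1.6 adds a press on a symptom. Section 8.8 refers to presses made every day. A subject can do both. The note in 8.8 also follows the LINQ II heading, while 6.1.6 concerns a device described as triggering the LINQ ICM, so the two may not even govern the same presses. There is a missing link but no contradiction.

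**2. Do the blank cells show that pre-loading QT data are absent?** Three visible points say no.
- Daily manual transmissions are marked at Baseline, and Section 6.1.7 says the transmitted data include ECG.
- The recording route that Section 6.1.8 ties to QT measurement is the Holter. It is marked at the index event, which may include a recording before the first dose.
- Section 7.3 speaks of patient activation and transmission in one phrase, so the schedule rows need not be separate activities.

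The inference that Baseline strips are all arrhythmia-triggered rests on Section 6.1, which is a general product description.

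**3. Where would the capture rules be?** In Sections 8.6 to 8.10, Table 2 and the flow diagrams. The public copy shows the headings, but almost none of that content. An absence there is not an absence from the plan.

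**4. What size could the effect be?** Inputs from Section 3.1: pre-treatment QTc of 446 ms (sotalol) and 469 ms (amiodarone); QTmax changes of 460 − 424 = 36 ms and 504 − 437 = 67 ms. Assumptions not in the document: heart rate HR of 60 to 70 bpm, a rate difference d between the periods, and no rate correction.

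Shift in raw QT = QTc × [(60/HR)^k − (60/(HR + d))^k], with k = 1/3 (Fridericia) or 1/2 (Bazett).

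| Case | Low end (446 ms, 70 bpm, k = 1/3) | High end (469 ms, 60 bpm, k = 1/2) |
|---|---|---|
| Whole pre-loading set, d = 5 | 9.6 ms | 18.4 ms |
| Whole pre-loading set, d = 10 | 18.44 ms | 34.79 ms |
| One symptom strip in eight, d = 10 | 18.44/8 = 2.31 ms | 34.79/8 = 4.35 ms |

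The share of one in eight assumes one symptom press for every seven daily presses, all in one period. If symptom strips were equally common in both periods, with the same rate difference, their effect would cancel. Against the 36 ms sotalol change, the diluted shift is 2.31/36 = 6% to 4.35/36 = 12%. The whole-set shift at d = 10 is 18.44/36 = 51% to 34.79/36 = 97%, but it requires every pre-loading strip to differ by 10 bpm. Rate correction would remove most of either shift.

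**The case for a change.** The best case for acting is that the blank cells are real, that the two unmarked rows are the very procedures named in the inclusion criteria, and that a 12-lead ECG is not LINQ ECG and so cannot serve an objective about detection from LINQ ECG. With at most 20 subjects and no replacement of those who exit, an unrecorded pre-loading period would be a permanent loss. Marking activations at Baseline would cost wording and a few button presses.

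Part of this stands. The reading of the cells is correct, the breathlessness instruction is unexplained, and a lost baseline would indeed be irrecoverable. But the argument needs patient-activated strips to be the QT data, and no visible passage says so; the route the protocol does name is the Holter. It also needs the index event to contain no pre-dose recording, which cannot be known while Section 8.7 is blank. The remedy has its own difficulty: it would extend to Baseline a set of capture conditions from Section 8.8 that cannot be read, and it could duplicate or clash with Sections 8.6 and 8.7. Rate correction is ordinary content for a statistical analysis plan, which was not available for this review.

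**Conclusion.** The concern does not call for a change. The observations about the schedule and Section 6.1.6 are accurate, but neither a missing baseline nor a bias follows from them, and no stated figure is affected. What is left is a sentence about breathlessness that the visible text does not tie to the QT objective. In a descriptive feasibility study with no hypothesis, that is a small gap that analysts can fill sensibly by deciding, and reporting, whether symptom-triggered recordings enter the summary. This assumes that those recordings can be told apart, which the visible text does not say. Under the assumptions above, leaving them in at one strip in eight moves mean raw QT by about 2.3 to 4.3 ms, and by less with rate correction.

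This conclusion rests on treating the blank sections as present in the full plan. It would change if Sections 8.6 and 8.7 and Table 2 turned out to provide no LINQ ECG suitable for QT measurement before the first dose.
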